**Anterior Bridging Cage With Bone Substitute Versus Localized Autobone in
Transforaminal Lumbar Interbody Arthrodesis**

NCT02485574

2021-07-14

Study protocol

Consecutive patients aged 18-80 years with spinal stenosis or spondylolisthesis who planned to undergo single-level lumbar transforaminal interbody fusion (TLIF) with pedicle screw fixation were included. All operations were performed at a single institution by a single surgeon. The enrolled patients had plain radiographs at postoperative 3, 6, and 12 months and fine-cut multiaxial reconstructed CT scan at postoperative 12 months to evaluate for bone-bridging patterns. The clinical outcomes were assessed by the Oswestry Disability Index (ODI) scores preoperatively and 12 months after surgery.

Operation Methods

After disc preparation following bilateral decompression with facetectomies, extra-cage bone grafting, consisting of half- mixed each 6 cc of local autobone and synthetic bone (OSTEON, Genoss, Korea), was performed on the prepared anterior disc space bilaterally; then, bilateral polyetheretherketone cages (ABB cage, Genoss, Korea) with different graft compositions (left cage: filled with local autobone, right cage: filled with local autobone + synthetic bone) were inserted.

Radiographic Fusion Criterion

We used the concept of InCBB and ExCBB to evaluate the fusion status. InCBB was defined as the bridging bone between the upper and lower vertebrae through the void of the cage(s) and divided into right (Rt.) and left (Lt.) InCBB according to the cage position. ExCBB was defined as the bridging bone between the 2 vertebrae in extra-cage areas of the disc space and divided into 5 zones based on their relative positions to the cages in the disc space: anterior ExCBB: front of the cage; posterior ExCBB: back of the cage; intermediate ExCBB: between 2 cages; right: at the right side of the right cage; and left ExCBB: at the left side of the left cage. We graded bridging scores from 0 to 2 based on the degree of completion of the bridging bone in InCBBs and ExCBBs (grade 0: no bridging at the superior and inferior endplates; grade 1: incomplete bridging; bridging at the superior or inferior endplate, but with a clear radiolucent line; grade 2: complete bridging). We defined ABB as the bridging bone between the extra-cage grafted bone and intra-cage grafted bone through the medial, lateral, superior, and inferior holes in each cage.

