InCBB, ExCBB and ABB were evaluated using a software program (Extended Brilliance Workspace 4.5 workstation, V4.5.2.4031, Philips Healthcare Nederland BV, the Nether- lands) that allows users to control the axis of the image planes. Three planes were set at each level as follows: the axial plane was set parallel to the operated disc space on coronal and sagittal views; the sagittal plane was set perpendicular to the disc space on coronal view and the posterior margin of the vertebrae on axial view; and the coronal plane was set perpendicular to the disc space on sagittal view and parallel to the posterior margin of the vertebrae on the axial view. The sagittal and coronal views were then serially examined for ExCBBs and InCBBs. The fusion was defined as meeting the following 3 criteria: no subsidence of 3 mm or more on serial postoperative 3, 6, 12 months radiographs until postoperative 12 months; at least having one or more grade 2 among InCBBs or ExCBBs (InCBB/ExCBB: 0/2, 1/2, 2/2, 2/1, 2/ 0); and the complete bridging bone, graded 2, should be confirmed on both sagittal and coronal views simultaneously. After three planes (sagittal, coronal, and axial) were set at each level, the sagittal and coronal views were serially examined for ExCBBs, InCBBs, and ABBs. To evaluate medial and lateral ABBs, we adjusted the sagittal plane on the axial view in a direction parallel to the diagonal axis of the cage.

Statistical Analysis

The differences between the fused and non-fused groups based on our suggested criterion were examined using independent t-tests for continuous variables. A P value <0.05 was considered statistically significant. All statistical analyses were performed using SPSS version 23.0 (SPSS, Chicago, IL, USA).

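### No planned analysis compares the two cage grafts, although the title and the operation are built around that comparison

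*Combined protocol and SAP*

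**What the plan says.** The title reads "Anterior Bridging Cage With Bone Substitute Versus Localized Autobone in" transforaminal lumbar interbody arthrodesis. No objective or hypothesis is stated anywhere.

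Operation Methods gives each patient two cages with different contents: "left cage: filled with local autobone, right cage: filled with local autobone + synthetic bone". A mixture of local autobone and synthetic bone was also placed outside the cages, and this grafting "was performed on the prepared anterior disc space bilaterally".

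Radiographic Fusion Criterion records in-cage bridging (InCBB) by side, "divided into right (Rt.) and left (Lt.) InCBB according to the cage position", and extra-cage bridging (ExCBB) in five zones. On the scale it says: "We graded bridging scores from 0 to 2 based on the degree of completion of the bridging bone in InCBBs and ExCBBs". Fusion requires subsidence to stay under 3 mm, "at least having one or more grade 2 among InCBBs or ExCBBs", and that a grade 2 "should be confirmed on both sagittal and coronal views simultaneously".

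Statistical Analysis has three sentences: one on the comparison, one on the 0.05 threshold and one on the software. The comparison is: "The differences between the fused and non-fused groups based on our suggested criterion were examined using independent t-tests for continuous variables".

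**The concern.** A title with a versus in it, and deliberately different fillings in the two cages of the same patient, point to a within-patient comparison of grafts. The side-specific grades needed for it are defined. The analysis section instead compares patients classified by outcome, fused against non-fused, and both groups contain both grafts.

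The only named test is also for continuous variables. No method is given for the 0–2 grades or for complete bridging as yes/no, and an independent-samples test would not suit right and left grades from one patient.

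At stake is the credibility of any statement about the bone substitute. It would rest either on an analysis whose endpoint and method were open to choice after the data were seen, or on a fused/non-fused contrast that does not compare the grafts.

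**Working it through.** The plan states no sample size, rate or effect size, so there is no figure to reproduce. The check is structural: can the fused/non-fused label reflect which cage bridged?

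**Inputs** (Radiographic Fusion Criterion): 7 graded sites, made up of 2 InCBB (right, left) and 5 ExCBB zones, each graded 0, 1 or 2. The bridging criterion is met if at least one site is grade 2. Each grade 2 is taken as confirmed on both views. Subsidence is a property of the operated level, not of a side, so it is set aside here and does not alter the symmetry.

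**Counts**

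- All patterns: 3^7 = 2,187.
- No grade 2 anywhere: 2^7 = 128. Bridging criterion met: 2,187 − 128 = 2,059.

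| Complete bridging in the cages | Patterns | Criterion met | Criterion not met |
|---|---|---|---|
| Right only | 1 × 2 × 3^5 = 486 | 486 | 0 |
| Left only | 2 × 1 × 3^5 = 486 | 486 | 0 |
| Both | 1 × 1 × 3^5 = 243 | 243 | 0 |
| Neither | 2 × 2 × 3^5 = 972 | 844 | 2 × 2 × 2^5 = 128 |
| Total | 2,187 | 2,059 | 128 |

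**Reading the table**

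1. A paired comparison of complete bridging draws its information from the discordant rows, 486 + 486 = 972 patterns. All 972 meet the bridging criterion, so the label cannot tell right-only from left-only.
2. Swapping the right and left cage grades changes the result in 0 of 2,187 patterns.
3. In 844 patterns the criterion is met through an extra-cage zone alone, with neither cage completely bridged. Those zones surround both cages and received the same mixed graft, so they do not separate the fillings.

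**Illustration on assumed rates.** Suppose complete bridging occurs independently, at 70% in the left cage, 50% in the right cage and 60% in at least one extra-cage zone. The share meeting the criterion is 1 − 0.3 × 0.5 × 0.4 = 94.0%. Reverse the cages (left 50%, right 70%) and it is 1 − 0.5 × 0.3 × 0.4 = 94.0% again. With 30% for the extra-cage zones, both orders give 1 − 0.3 × 0.5 × 0.7 = 89.5%. Opposite graft results produce the same fused share. The rates are invented for the illustration, and the conclusion does not depend on them.

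**Other outcomes.** The Oswestry Disability Index is one score per patient, and each patient has both grafts, so it cannot separate them either.

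**The case against.** The strongest reply has four parts.

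- **The purpose may be different.** With no stated objective, the graft comparison is inferred. The CT scans are described as serving the study of bridging patterns, and the fused/non-fused contrast fits an aim of examining the proposed fusion criterion. This stands in part: the contrast may serve that aim. But that aim does not explain the title or the different fillings by side.
- **Side-specific results may still appear.** The continuous variables to be tested are not listed and could include the right and left InCBB scores; rates by cage could also simply be tabulated. That is true, so the symmetry shown above is a property of the fusion label and not of every table built on it. Still, comparing each cage's score between fused and non-fused patients does not test one filling against the other, and InCBB grade is itself part of the fusion definition. A possible tabulation is not a planned contrast.
- **The remedy is imperfect.** Graft is fixed to side, no randomisation of side is described, and the extra-cage mixture is shared. A paired analysis therefore estimates graft and side together, for a narrower question than the title suggests. This stands in full and has to be reported with the result.
- **It may be too late.** The text is in the past tense. If the data have been seen, new wording cannot restore prespecification. This also stands, and it calls for a post hoc label.

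It is also fair to say that the pattern counts restate the fusion rule and do not measure harm to a result.

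**Conclusion.** The concern holds. The plan specifies no test, estimate or interval for autobone plus synthetic bone against autobone alone, and its one stated contrast groups patients by a label that is indifferent to side: 0 of 2,187 patterns change when the cages are swapped, and all 972 one-cage-only patterns get the same result.

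This rests on the fusion definition as written and on reading the title and the two fillings as implying a graft comparison. It needs no assumed rates. Nothing is claimed about effect size or power, because the documents give no sample size or bridging rates. The gap lies in the analysis plan and not in the measurements, and it must be closed before any conclusion about the graft is drawn.

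**What to change.** 1. State the objective. If it includes the graft, define the contrast as in-cage autobone plus synthetic bone versus in-cage autobone alone, with the mixed extra-cage graft present on both sides.
2. Make the main graft analysis a within-patient comparison of right and left complete InCBB at 12 months (grade 2 confirmed on both views). A suitable method is McNemar's test with the paired risk difference and its 95% confidence interval. Publish the full paired table, including both discordant counts.
3. Support it with a paired ordinal test on the 0–2 grades, for example the Wilcoxon signed-rank test.
4. State that graft is fixed to side with no described randomisation of side, so the estimate combines graft and side effects.
5. Label the analysis post hoc if it is specified after the data were seen.
6. Report patient-level fusion, ExCBB and the disability score as outcomes of the whole construct, not as graft comparisons.
7. Compare bridging through the cage holes (ABB) by side only if a score per cage is first defined; the 0–2 scale is stated for InCBB and ExCBB only.

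The cost is low: a few sentences in the SAP and one additional table from grades already collected, with no new imaging. The price is an openly stated limitation on side and possibly exploratory status. An ABB comparison would also need a new score definition.

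### If the fused versus non-fused t-test covers ODI, the plan does not say which ODI quantity is tested and states no adjustment for the preoperative ODI it collects

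*Combined protocol and SAP*

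**What the plan says.** The Study protocol section states: "The clinical outcomes were assessed by the Oswestry Disability Index (ODI) scores preoperatively and 12 months after surgery". No other clinical outcome is named.

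The Statistical Analysis section has three sentences. The analysis sentence is "The differences between the fused and non-fused groups based on our suggested criterion were examined using independent t-tests for continuous variables". The other two give the threshold, "A P value <0.05 was considered statistically significant", and the software, "All statistical analyses were performed using SPSS version 23.0". None of the three mentions ODI, a change score, a covariate or a paired comparison, or says whether equal or unequal variances are assumed.

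The groups being compared are defined under Radiographic Fusion Criterion. One requirement is "no subsidence of 3 mm or more on serial postoperative 3, 6, 12 months radiographs until postoperative 12 months". The others concern complete bridging bone, judged on the "fine-cut multiaxial reconstructed CT scan at postoperative 12 months to evaluate for bone-bridging patterns". The graft contrast itself, under Operation Methods, is between cages in the same patient: "left cage: filled with local autobone, right cage: filled with local autobone + synthetic bone".

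**The concern.** ODI is the only named clinical outcome, so it is natural to read the unnamed continuous variables as including it. The t-test can then be run on the 12-month score or on the change from before surgery. The plan does not choose, and neither version adjusts for preoperative ODI.

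In a randomised comparison this would mainly cost precision. Here the groups are formed after surgery by how the bone healed. Nothing in the design balances preoperative ODI between patients who fuse and patients who do not. An ODI difference could therefore partly reflect who was worse before surgery, and its size, or even its sign, could depend on an unstated choice that can be made after the data are seen.

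**Working it through.** **No figure to reproduce.** The documents give no sample size, group split, SD, correlation or effect size for ODI. Step 1 is an identity and needs no assumption about any of these. The inputs to steps 2 to 5 are assumed for illustration, and none of the results is an error rate for this study.

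**1. Gap between the two t-tests.** Write X for preoperative and Y for 12-month ODI, with differences taken as non-fused minus fused in patients who have both scores.
- 12-month test: D_Y = mean Y (non-fused) - mean Y (fused)
- Change test: D_C = D_Y - D_X
- Gap: D_Y - D_C = D_X, the preoperative difference, exactly

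**2. Size for an assumed imbalance.** Assume D_X = 5 points, equal SDs at both times, pre/post correlation r = 0.3 to 0.6, and equal expected 12-month ODI for patients with equal preoperative ODI.

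| r | 12-month test, 5 × r | Change test, 5 × (r - 1) | Gap |
|---|---|---|---|
| 0.3 | +1.5 | -3.5 | 5 |
| 0.6 | +3.0 | -2.0 | 5 |

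The two tests point in opposite directions although the adjusted difference is zero by construction.

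**3. Could 5 points arise by chance alone?** Assume N = 50 and preoperative SD 12 to 18. SE = SD × sqrt(1/n1 + 1/n2).
- Split 43/7: SE = 4.89 to 7.34; probability of a difference of 5 points or more in either direction, 31% to 50%
- Split 40/10: SE = 4.24 to 6.36; probability 24% to 43%

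This is chance only. Any real link between preoperative ODI and healing would add to it.

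**4. Precision.** Relative to the 12-month score (variance 1), with equal SDs, the change score has variance 2(1 - r) = 1.4 at r = 0.3 and 0.8 at r = 0.6. The adjusted model has 1 - r² = 0.91 and 0.64. Allowing for estimation of the slope at N = 50, multiply by 1 + 1/(50 - 4) = 1.022, giving 0.93 and 0.65. Adjustment thus removes a net 7% to 35% of the variance of the 12-month comparison.

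**5. Unequal variances.** Simulation with normal data, nominal 5%, and non-fused/fused SD ratios from 0.5 to 2:
- t-tests at 45/5: pooled 0.1% to 25.1%; Welch 5.4% to 5.8%
- Adjusted model at 44/6: ordinary standard errors 0.2% to 23.5%; HC3 (heteroscedasticity-consistent) 4.7% to 7.6%
- Adjusted model at 40/10: ordinary 0.5% to 18.3%; HC3 4.2% to 6.1%

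The extremes come from SD ratios of 0.5 and 2. With equal SDs at 44/6, ordinary standard errors hold about 5% and HC3 gives about 6%. HC3 is thus slightly worse when variances are equal and much safer when they are not.

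**The case against.** **ODI may not be tested at all.** The analysis sentence does not name it. That stands, and it is why the point is conditional. If ODI is not compared, the only named clinical outcome has no stated analysis, and the plan should say so.

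**Preoperative ODI may have a role.** A reader might infer that it has none. The documents do not support that: it is itself continuous, so the unrestricted wording could include a comparison of preoperative ODI between the groups. What can be said is that no adjustment is stated, and that the plan does not say whether or how preoperative ODI enters.

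**When the groups become known.** A reader might also infer that group membership is known only at the 12-month visit. That is wrong. Subsidence of 3 mm or more at month 3 or 6 already makes a patient non-fused; only fused status has to wait for the 12-month images. The concern does not need the stronger statement. It is enough that the groups are postoperative and not randomised.

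**The illustration favours adjustment.** Step 2 assumes equal 12-month ODI at equal preoperative ODI, which is the null hypothesis of the adjusted model. It therefore cannot show that model to be better than a change score. This stands. A pre-stated change-score comparison would also remove the ambiguity, but it answers a different question in non-randomised groups and still depends on the imbalance.

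**The contrast is peripheral.** It does not address left versus right cage, so the point is a modest one. The documents do not rank outcomes as primary or secondary; placing this contrast behind the graft question is a judgement from the title and design.

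**Conclusion.** The point holds as a gap in specification with an inexpensive improvement available. If ODI is compared between fused and non-fused patients, the quantity tested is unstated and no adjustment for preoperative ODI is planned, in groups where baseline balance cannot be presumed.

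That the two t-tests differ by the preoperative difference is exact. The magnitudes are not: the 5-point imbalance, SDs, correlation, N = 50, splits, SD ratios and normality are all assumed. On those assumptions the unstated choice moves the result by 5 points and can reverse its sign.

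The documents do not show that preoperative ODI was in fact unbalanced, that a reported ODI result is biased, or that the study's error rate departs from 5%. Nor would adjustment make the contrast causal. Importance is modest; confidence is medium, because it is uncertain whether ODI is among the variables tested.

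**What to change.** State in the Statistical Analysis section whether ODI is compared between fused and non-fused patients. If it is:

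- Analyse 12-month ODI by linear regression on fusion status with preoperative ODI as covariate, and report the adjusted difference with its 95% CI.
- Use standard errors that allow unequal variances (for example HC3), since the groups may differ in size and spread. For other continuous variables, read the unequal-variance (Welch) result.
- If only a handful of patients are non-fused, interpret the result cautiously. No fixed count is proposed: the documents give no sample size from which to justify one.
- Label the contrast an observational association that other factors, such as age or diagnosis, may still confound, and that does not answer the left-versus-right graft question.
- Label the model post hoc if the data have already been analysed, as the document's past tense suggests they may have been.

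The cost is a few sentences of text, one degree of freedom and a short re-analysis. The covariate is already collected. Check that the stated software can produce the standard errors; if it cannot, another package is needed.

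### Does the unlisted set of t-tested variables make the fused versus non-fused comparison circular?

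*Combined protocol and SAP*

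**What the plan says.** The Statistical Analysis section has three elements: a test, a threshold and the software. The test is: "The differences between the fused and non-fused groups based on our suggested criterion were examined using independent t-tests for continuous variables". The threshold is: "A P value <0.05 was considered statistically significant". No variable is listed, and no method is given for ordinal or categorical data.

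The two groups come from the Radiographic Fusion Criterion section. A patient is fused if three conditions hold:

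- The first concerns cage settling: "no subsidence of 3 mm or more on serial postoperative 3, 6, 12 months radiographs until postoperative 12 months".
- The second concerns bridging grade: "at least having one or more grade 2 among InCBBs or ExCBBs".
- The third concerns how that grade is verified: "the complete bridging bone, graded 2, should be confirmed on both sagittal and coronal views simultaneously".

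On the scale of the bridging data the same section says: "We graded bridging scores from 0 to 2 based on the degree of completion of the bridging bone in InCBBs and ExCBBs". There are two InCBB sites (right and left cage) and five ExCBB zones, seven in all.

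Two other measures lie outside the three conditions. The Study protocol section says: "The clinical outcomes were assessed by the Oswestry Disability Index (ODI) scores preoperatively and 12 months after surgery". The other is ABB: "We defined ABB as the bridging bone between the extra-cage grafted bone and intra-cage grafted bone". It is given no grading scale.

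**The concern.** A test between two groups is informative only if the variable tested did not help to form the groups. Here a patient cannot be fused without at least one grade 2, and cannot be fused with subsidence of 3 mm or more. If zone grades or millimetres of subsidence were then t-tested between fused and non-fused patients, their means would differ by construction. A small P value would partly repeat the criterion.

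Three features make this more than a remote worry. The plan lists no variables. It calls the grades scores and offers no other test for them. And CT is done in order to describe bridging patterns, so a table of zone grades by fusion status is a natural thing to produce. Right and left InCBB also correspond to the two cage fillings. A P value for either one, fused against non-fused, could be misread as evidence about graft composition, which is the subject of the title.

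**Working it through.** The plan states no sample size, rate, SD or effect, so it has no figure to reproduce. The check has two parts: what the text commits to, and how large the built-in difference would be if the components were tested.

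**Part 1. Candidate variables against the wording**

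| Variable | Part of the fusion definition? | Continuous as the plan describes it? |
|---|---|---|
| ODI, preoperative and 12 months | No | Yes, a score |
| Age (eligibility 18-80 years) | No | Yes |
| ABB | No | No scale given |
| InCBB/ExCBB grades | Yes | No, ordered 0, 1, 2 |
| Subsidence | Yes | Used only as below 3 mm or not; no analysis in mm described |

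The variables that plainly fit the sentence are not circular. Each circular one needs a step the text does not take: treating a three-level grade as continuous, or analysing subsidence in mm.

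**Part 2. Size if the components were tested (all inputs assumed)**

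Assumptions: seven zone grades, subsidence and an outside variable, all mutually independent; P(grade 2) per zone p = 0.10 to 0.40; subsidence of 3 mm or more in a share s = 5% or 15%; N = 30, 50 or 100; two-view confirmation counted as part of grade 2.

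Write q1 for P(grade 1). Then:

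- P(no grade 2 in any zone): A = (1 − p)^7
- P(fused): F = (1 − A)(1 − s)
- mean grade of one zone: m = q1 + 2p
- mean if fused: mF = [m − A·q1/(1 − p)]/(1 − A)
- mean if not fused: mN = (m − F·mF)/(1 − F)

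With p = 0.25, q1 = 0.30, s = 0.05:

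- A = 0.75^7 = 0.1335
- F = 0.8665 × 0.95 = 0.823
- m = 0.80
- mF = (0.80 − 0.1335 × 0.40)/0.8665 = 0.862
- mN = (0.80 − 0.823 × 0.862)/0.177 = 0.513 (unrounded inputs)
- difference = 0.35

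With p = 0.40, q1 = 0.30, s = 0.15:

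- A = 0.6^7 = 0.028
- F = 0.972 × 0.85 = 0.826
- m = 1.10
- mF = (1.10 − 0.028 × 0.50)/0.972 = 1.117
- mN = (1.10 − 0.826 × 1.117)/0.174 = 1.018 (unrounded inputs)
- difference = 0.10

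These are the largest and smallest differences over the assumed grid.

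Share of simulated pooled t-tests with P<0.05 over the grid (4,000 replicates per cell, subsidence drawn from a gamma distribution with shape 2; replicates with fewer than two patients in a group were skipped):

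| Variable tested | Share with P<0.05 |
|---|---|
| One named zone grade | 5.5% to 60% |
| At least one of seven zone grades | 32% to 99.9% |
| Subsidence in mm | 9% to 100% |
| Variable outside the definition | 4% to 6% |

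For the second row, seven valid independent tests would give 1 − 0.95^7 = 30%.

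The pattern depends on why patients fail. At N = 50, p = 0.10 and s = 5%, a zone grade is significant in 33% of runs and subsidence in 14%. At N = 50, p = 0.40 and s = 15%, the figures are 6% and 99.8%. A separate simulation with a normal-based subsidence distribution and N of 40 or 80 gave 9% to 45% for a zone and 6% to 86% for subsidence, again with 4% to 6% for an outside variable.

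These percentages are not type I error rates. When a variable helps to define the groups the means truly differ, so they show how often a built-in difference is detected.

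**The case for a change.** The strongest case for a change is that the omission is certain and a list of variables would cost one sentence. The bridging data are the main radiographic product of the study. If continuous excludes the grades, the plan has no test for them at all. If it includes them, the comparison is circular. Subsidence is judged against a millimetre threshold, so it is presumably measured in mm and could count as continuous even on a strict reading.

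Part of this stands. The variables are not named, the components do define the groups, and a P value for a component would not be independent evidence. What does not follow is that the plan produces such P values. Having no test for the grades is compatible with reporting them descriptively, which is the sensible treatment of components of the definition. The text gives subsidence no role beyond the cut-off. The case therefore rests on an analysis that might be run, not on one that is planned.

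A comparison of the two cage fillings within patients is a different question. It neither follows from this point nor adds weight to it.

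**Conclusion.** The concern does not call for a change. Followed as written, the plan compares continuous variables between fused and non-fused patients. ODI meets that description without circularity, and a variable outside the definition kept its nominal error rate in the simulations (4% to 6%). The unlisted variables are a gap that a competent analyst fills sensibly: test what lies outside the criterion, and describe what lies inside it.

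One caution for reading the results: if a report gives P values for InCBB/ExCBB grades or subsidence by fusion status, they should be taken as descriptive of the criterion. The built-in difference in one zone's mean grade would be 0.10 to 0.35 points under the assumed inputs. The rejection rates run from near nominal to certainty because the documents fix none of N, zone rates, subsidence distribution or fusion rate, and independence between zones of one disc space is also an assumption. The figures illustrate the mechanism and do not estimate an effect in this trial.

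### No primary endpoint, no list of tested readouts and an unadjusted 0.05 threshold, while the only stated test does not make the title's graft comparison

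*Combined protocol and SAP*

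**What the plan says.** The Statistical Analysis section of the combined protocol and SAP has three sentences. The first gives the only test: "The differences between the fused and non-fused groups based on our suggested criterion were examined using independent t-tests for continuous variables". The variables are not listed. The second gives the threshold: "A P value <0.05 was considered statistically significant". The third names the software. No endpoint is called primary, and there is no ordering of endpoints or multiplicity adjustment.

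Operation Methods puts the graft contrast inside each patient: "left cage: filled with local autobone, right cage: filled with local autobone + synthetic bone".

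Radiographic Fusion Criterion describes the bridging readouts:
- InCBB is "divided into right (Rt.) and left (Lt.) InCBB according to the cage position".
- ExCBB is "divided into 5 zones based on their relative positions to the cages in the disc space".
- ABB is read "through the medial, lateral, superior, and inferior holes in each cage".

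InCBB and ExCBB are graded 0 to 2; no scale is given for ABB. Fusion is a composite ("The fusion was defined as meeting the following 3 criteria"), and one criterion is a grade 2 at one or more InCBB or ExCBB sites. For function, "The clinical outcomes were assessed by the Oswestry Disability Index (ODI) scores preoperatively and 12 months after surgery".

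**The concern.** Two gaps meet here.

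- **The stated test answers a different question.** Comparing fused with non-fused patients shows how those groups differ. It says nothing about whether the cage with synthetic bone bridges as well as the cage with local bone alone. Every patient has both cages, so that question needs a within-patient right-left comparison, and the plan gives none.
- **The choice of what to test is open.** The document describes many sites, applies one unadjusted threshold and does not say which sites are tested. The sponsor could examine all of them and present whichever pair, hole or zone falls below 0.05. A reader could not tell how many comparisons lay behind that result.

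At stake is whether the title's question gets one answer with a stated error rate, or an answer selected after the data were seen.

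**Working it through.** The documents state no sample size, overall alpha or number of tests, so there is no figure of the plan's own to reproduce. The check counts what could be tested and shows how the error rate depends on that count.

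**Inputs**
- Per-test threshold 0.05 (Statistical Analysis).
- InCBB: 2 sites. ExCBB: 5 zones. ABB: 4 holes × 2 cages = 8 (Operation Methods and Radiographic Fusion Criterion).
- ODI: preoperative and 12 months (Study protocol).

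**Step 1: possible families**
- Right-left pairs: InCBB (1), lateral ExCBB (1), ABB holes (4) = 6. The anterior, posterior and intermediate ExCBB zones, fusion and ODI have no right-left counterpart.
- Eight ABB holes plus 12-month ODI, fused versus non-fused = 9. This leaves out the 7 InCBB and ExCBB grades, which help define fusion.
- Every described site plus 12-month ODI: 2 + 5 + 8 + 1 = 16, or 17 with preoperative ODI.

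**Step 2: chance of at least one false positive**

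For k independent tests with every null true, the chance is 1 − 0.95^k.

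| Family | k | 1 − 0.95^k |
|---|---|---|
| 12-month ODI only | 1 | 0.050 |
| ODI at both times | 2 | 0.098 |
| Right-left pairs | 6 | 1 − 0.735 = 0.265 |
| ABB holes + ODI | 9 | 1 − 0.630 = 0.370 |
| All sites + ODI | 16 | 1 − 0.440 = 0.560 |
| As above + preoperative ODI | 17 | 1 − 0.418 = 0.582 |

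The chance passes one half only from k = 14 (0.512; k = 13 gives 0.487).

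**Step 3: correlation**

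Surgery is at a single level, so all sites in a patient lie in one disc space and positive correlation is plausible. The documents give no value, so the correlations here are assumed. A simulation of 16 equally correlated two-sided normal tests (400,000 draws per setting) gives 0.515 at correlation 0.2, 0.477 at 0.3, 0.374 at 0.5 and 0.264 at 0.7. Positive correlation likewise lowers the figures for 6 and 9 tests, so 26.5% and 37% are upper values for those families.

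**Step 4: test against question**

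The stated test groups patients by fusion status. The graft contrast does not vary between patients, because each has both grafts. No fused versus non-fused result can therefore estimate the graft difference, however many readouts are tested.

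**The case against.** The strongest objection is that the text never says all the readouts are tested. The threshold follows a single test type, limited to continuous variables. ODI is the only described outcome that is plainly continuous. On a literal reading the family could be one or two tests, with an error rate of 5% or 9.8%. The InCBB and ExCBB grades help define the fused group, so a fused versus non-fused difference on them is partly built in and a true-null error rate does not apply. Fusion status is the grouping variable and cannot be an outcome of that test. Finally, P<0.05 is a per-test threshold; the plan promises no family-wise rate, and adjustment in a study of this kind can be debated.

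Most of this stands, and it rules out a stronger reading. A reader might infer that every one of 16 or 17 readouts is judged at 0.05, so that a false positive somewhere is more likely than not. The documents do not support that. It needs at least 14 tests, all independent, on outcomes that include the seven grades behind the fusion split.

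The objection does not remove the gap. The literal reading leaves the graft question untested, and any wider reading leaves the number of tests to be settled later. The document neither calls itself exploratory nor commits to a single test.

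**Conclusion.** The point holds in a limited form. The plan has no primary endpoint, no list of tested readouts and no multiplicity control, and its one stated test does not address the comparison in its title.

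The size of the multiplicity problem depends on a family that the plan does not define. The family closest to the title question is the six right-left pairs, at up to 26.5%. These figures assume that each member is tested at 0.05 and that every null is true; independence gives the upper value.

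The mismatch between test and question does not depend on any of these figures. It should be corrected even if only one or two tests were ever intended.

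**What to change.** Replace the test description with a short ordered plan:

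1. **Primary:** complete (grade 2) InCBB at 12 months, right versus left cage, by a paired test such as McNemar's, at two-sided 0.05. Report the paired difference in proportions with its 95% CI.
2. **Secondary:** the other five right-left pairs (lateral ExCBB and the four ABB holes). Either apply Holm's procedure, whose first step is 0.05/5 = 0.01, or report estimates with 95% CIs. State the scale on which ABB is recorded.
3. **Descriptive:** fusion, ODI, the non-lateral ExCBB zones and all fused versus non-fused comparisons, with 95% CIs and no claim of significance. These do not belong in the Holm family, because they have no right-left contrast.
4. **Timing:** the document is written in the past tense. If the outcome data have already been seen, label the choice of primary as post hoc; adding it then does not restore prespecified error control.

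The cost is a few sentences in the Statistical Analysis section and no new data, since these sites are already part of the planned CT assessment. The downside is that fewer secondary results can be called significant. The documents give no sample size, so the power of the paired test cannot be judged from them.
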